5.2.2 Secondary Endpoint(s)

Secondary endpoints include the sensitivity, specificity, positive predictive value and negative predictive value of Cytosponge both overall, and stratified by baseline histology and length of BE. The presence of BE will be defined as per ACG guidelines, with histology interpreted by the home institution. Additional secondary outcomes include degree of mucosal abrasion and safety data.

6. Study Design

This is a cross-sectional study of subjects with BE to assess the utility of the Cytosponge device as a nonendoscopic method for sampling surface cells from the esophagus. Patients presenting for routine endoscopic BE surveillance examinations, planned ablation or examinations investigating chronic GERD symptoms will be offered enrollment in the study. After informed consent, and on the same day as the planned standard of care endoscopic procedure, the subject will undergo administration of the

COVB2710467

Version G 01-DEC-2017

Page 17 of 61

Cytosponge device and then complete questionnaires. The subject will then undergo standard of care upper endoscopy with or without biopsy. The biopsy protocol will be performed according to accepted recommendations. For subjects presenting for GERD, a single set of 4 quadrant biopsies (4 pieces of tissue total) of the gastric cardia (TGF+1) will be collected during the endoscopy procedure. If for some reason a biopsy is not taken, the subject will still count toward enrollment and their data will be used in the final data set. It is encouraged for Investigators to take photos of the gastroesophageal junction (GEJ) during the endoscopy procedure.

The Cytosponge will be placed in fixative and shipped to an accredited pathology laboratory for processing will provide results on each sample. Cardia biopsies and routine care tissue biopsies will undergo standard processing and hematoxylin and eosin (H&E) staining at the home institutions, with assessment by expert pathologists. Subjects will be contacted via phone 7 days (+/-3days) after Cytosponge administration to complete an additional questionnaire and assess adverse events. For quality assurance, Cytosponge samples may be sent to the to be processed and read, as needed to optimize training at the central lab. These results will be compared to those reported by for the results are conflicting, for training may be revisited and consensus read will be used.

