Enrolled subjects will be administered the Cytosponge one time, on the date of an endoscopy scheduled for routine care, prior to the endoscopy. Subjects can only participate one time. The only exception is for subjects who have an inadequate sample on the initial Cytosponge. These subjects will be asked to return for repeat Cytosponge administration after the initial administration.

All subjects taking part in the study will be undergoing an endoscopy as part of standard of care, the risks of the study are all linked with the administration of the Cytosponge, and are extremely low as no Cytosponge I related serious adverse events have been reported in subjects from the BEST1 study (n=504) and/or BEST2 (to date n=1500)².

The results from this study will not be used to influence patient management or follow-up.

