6.1. Duration

Participation in the study may last about4-10 days after the procedure. Subjects will be contacted 7 days (+/- 3 days) following the Cytosponge and upper endoscopy procedures. During this phone call, adverse events will be assessed and subjects will complete final questionnaire. Participation in the study is complete when subjects have completed the follow-up phone call.

If the Cytosponge tissue specimen is reported as inadequate by the central pathologist, the subject will be asked to return for repeat Cytosponge administration. Only the Cytosponge[™] Cell Collection capsule administration will be repeated. Questionnaires and the endoscopy procedure will not be repeated.

The study is expected to last a total of 24 months (2 years).

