9.1. Schedule of Events

Assessment	Screening/Enrollment Visit	Follow-Up Phone Call (7 days +/- 3 days after Enrollment)	Repeat Cytosponge
Informed Consent Form	х		
Demographics	X		
Medical History	X		
Inclusion/Exclusion Criteria	x		
Cytosponge Administration	x		\mathbf{X}^1
Visual Analog Scale	X ²		
Routine Care Endoscopy with Biopsy	X ^{3,4}		
Impact of Event Scale		X	
Procedure Preference and Acceptability Questionnaire		x	
Adverse Events ⁵	Х	X	Х

¹If the initial Cytosponge sample is inadequate, sites will be notified and subjects will be asked to return for repeat Cytosponge administration. Only the Cytosponge administration will be repeated. Questionnaires and the endoscopy procedure will not be repeated on these patients.

²VAS should be administered immediately following completion of the Cytosponge and prior to the upper endoscopy.

COVB2710467

Version G 01-DEC-2017

³Routine care biopsies should be taken during the endoscopy following the Cytosponge as this is considered standard of care for the target population.

⁴For subjects presenting for GERD, a single set of 4 quadrant biopsies (4 pieces of tissue total) of the gastric cardia (TGF+1) should be taken for this research study. The research specific biopsies will be taken in addition to any routine care biopsies taken during the procedure and will still be obtained even if routine care biopsies are not taken. The Sponsor will pay for any charges related to collection and pathology of the research specific gastric cardia biopsies.

It is encouraged for Investigators to take photos of the gastroesophageal junction (GEJ) during the endoscopy procedure.

⁵Every adverse event must be reported to the sponsor and recorded in the electronic case report form. Sites are responsible for following local IRB guidelines for reporting adverse events to their local IRB.

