10.1. Potential Risks

There are several possible risks that could occur when swallowing the Cytosponge capsule which include but are not limited to:

- Aspiration (accidentally inhaling material from the stomach into the lungs) and/or airway obstruction are possibilities but these risks are expected to be minimal.
- Although the sponge is soft, possible risks include, bleeding, pain, vomiting, sore/irritated throat, and burning sensation from any mucosal surfaces of the mouth, stomach or esophagus (swallowing tube) which comes in contact with the sponge.
- Laceration of any mucosal surface coming into contact with the sponge is possible, including mucosal surfaces of the stomach, esophagus, throat or mouth. Although very unlikely, perforation of the stomach or esophagus is also possible which could require secondary intervention.
- Although the risk has been found to be 2%, sponge detachment from the suture could also occur. Should this occur, the sponge will be retrieved during the planned endoscopy that follows administration of the sponge. Although not observed in previous Cytosponge studies the risk of infection or intestinal obstruction is a possibility.

The current study has been designed to minimize occurrence of these potential risks by use of the exclusion criteria. Most subjects enrolled in this study will have previously received an upper endoscopy, which will document the absence of esophageal varices and strictures. During administration of the sponge, the patient is not sedated and the device does not render the upper esophageal sphincter incompetent. These elements further reduce the overall risk for serious adverse events.

All serious adverse events, which, based on the investigator's judgment, are considered to be device related, should be reported to Medtronic-GI Solutions within 24 hours after the investigator is made aware of the event.

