G •	 surfaces of the mouth, stomach or esophagus (swallowing to comes in contact with the sponge. Laceration of any mucosal surface coming into contact sponge is possible, including mucosal surfaces of the esophagus, throat or mouth. Although very unlikely, per the stomach or esophagus is also possible which coursecondary intervention. Although the risk has been found to be 2%, sponge detachmer suture could also occur. Should this occur, the sponge will be during the planned endoscopy that follows administration of the Although not observed in previous Cytosponge studies infection or intestinal obstruction is a possibility. The current study has been designed to minimize occurrence of potential risks by use of the exclusion criteria. Most subjects er this study will have previously received an upper endoscopy, wildocument the absence of esophageal varices and strictures. Du administration of the sponge, the patient is not sedated and the does not render the upper esophageal sphincter incompetent. elements further reduce the overall risk for serious adverse ever BE arm biopsies are required during standard upper endoscopy Although the risk has been found to be 2%, sponge detachment suture could also occur. dated Revision to Rev. F and Revision date to 23.Sept.2016 Investigation Purpose: ADD GERD: To assess the utility of the Cytosponge device as a non-endoscor method for collecting surface cells from the esophagus in patient and GERD Primary Objective(s): Remove "within the last 5 years": To assess the acceptability of a novel, minimally invasive esophagus in patient and GERD 	ube) which t with the s stomach, foration of uld require nt from the e retrieved he sponge. the risk of f these nrolled in hich will uring e device These ents t from the opic ents with BE Clin Spe- hageal dergoing	Sr. ical Project cialist
•	 mucosal sampling technique, the Cytosponge 1) in subjects und surveillance of BE who have had at least a C1 or M3 segment co (or medically suspected), within the last 5 years, and 2) in subject GERD undergoing screening for BE. Sample Size: Increase the sample size by 100 subjects: 120 21 (Enrollment ratio of at least ≥50% BE and ≥25% GERD) _with BE (at least C1 or M3 confirmed at Cytosponge endoscop 55 subjects with GERD symptoms undergoing screening for BE. Inclusion Criteria: 4)a) Remove "in last 5 years" 	lergoing Reso onfirmed Species ects with 75 subjects py, and 75	earch cialist

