	metaplasia, and Prague classification of at least one circumference centimeter of BE or a total BE segment length of at least 3 centi	imeters	

COVB2710467

Version G 01-DEC-2017

(C1+ or CXM3+) (BE arm) in last 5 years. OR

- Updated Exclusion #3: Current use of anti-thrombotics (anti-coagulants and anti-platelet drugs) that cannot be safely discontinued for the appropriate drug-specific interval in the peri-administration period. Depending on the particular agent or reason for the anti-thrombotic therapy, it may not be necessary to discontinue anti-thrombotic agents. There could also be circumstances where the drug may not need to be discontinued if the risk of bleeding is considered negligible (e.g. daily aspirin therapy). Physicians should use their clinical judgment and should consult relevant guidelines such as those provided by the ASGE.
- Repeat sponge procedure: Remove 30 days later (+/- 10 days).
- Subjects will be contacted via phone 7 Days Change 2 days to 3 days: (+/-2 3 days).
- Lab processing remove time of lab processing: Samples will be shipped to an accredited pathology laboratory for processing before the end of the next business day.
- Add Appendix III: Healthy Volunteer ICF
- Remove Exclusion criteria #9: Planned ablation or resection therapy (including endoscopic mucosal resection and submucosal dissection) within 3 days after Cytosponge administration.
- Subjects who undergo same day ablative therapy (as Cytosponge testing) will Impact of Event Scale scores evaluated separately as opposed to the BE surveillance group.
- Secondary Objectives 2) Add: Patients who are undergoing ablative therapy on the day of Cytosponge testing must have biopsies within 2 months prior to surgery.

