Primary Objective(s)	 To assess the acceptability of a novel, minimally invasive esophageal mucosal sampling technique, the Cytosponge 1) in subjects undergoing surveillance of BE who have had at least a C1 or M3 segment confirmed (or medically suspected), and 2) in subjects with GERD undergoing screening for BE Patients who are undergoing ablative therapy on the day of Cytosponge testing will have their acceptability data analyzed separately. Based on previous data, we hypothesize that the spongebased sampling technique will be associated with low levels of subject distress, and will be preferred by subjects, when 	

Form Medtronic

Revision 2.0 Page 5 of 13

	compared to standard sedated upper endoscopy, for surveillance of their esophageal mucosa.
	 To assess the adequacy of cytology samples obtained by Cytosponge in this population after 1 sampling, or after 2 samplings if first sample is inadequate. Based on previous data, we hypothesize that the Cytosponge will harvest adequate amounts of esophageal cells to perform centrifugation, pelleting, sectioning and staining for trefoil factor 3, a reliable biomarker of intestinal metaplasia.
Secondary Objective(s)	 To assess the operating characteristics of this technique against a gold standard of upper endoscopy with biopsies for endoscopic surveillance in subjects with BE who demonstrate an adequate sample on Cytosponge assessment.
	2) To assess the operating characteristics of Cytosponge against the worst ever histology documented in the subject. Patients who are undergoing ablative therapy on the day of Cytosponge testing must have biopsies within 2 months prior to surgery. Because Cytosponge provides a "field" sampling of esophageal tissue, it may provide a more comprehensive assessment of minute fields of dysplasia. If this is so, the Cytosponge may avoid sampling error associated with random clinical samples as currently performed.
	3) To assess the operating characteristics of Cytosponge on the basis of baseline histology. To date, no data is available regarding the accuracy of Cytosponge in subjects with BE and more advanced disease (low-grade dysplasia and high-grade dysplasia). These subjects are at greatest risk for progression to cancer. We plan to collect pilot data on operating characteristics of the assay by degree of baseline dysplasia. We hypothesize that Cytosponge will perform with similar operating characteristics in this group compared to non-dysplastic BE.

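### The repeat-sponge rule has no exception for subjects ablated at the study endoscopy, so they could be recalled for a research-only sponge after treatment

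*Protocol*

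**What the plan says.** **Who is enrolled.** CIP section 6: "Patients presenting for routine endoscopic BE surveillance examinations, planned ablation or examinations investigating chronic GERD symptoms will be offered enrollment". The version history in CIP section 18 shows how planned ablation came in. Among the version G changes is "Remove Exclusion criteria #9: Planned ablation or resection therapy (including endoscopic mucosal resection and submucosal dissection) within 3 days after Cytosponge administration".

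**Order of events.** CIP section 6 places the single planned sponge on the day of the routine endoscopy and before it.

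**Repeat rule.** A first sample with no columnar cell on H&E triggers a second sponge. The rule appears in CIP section 6 ("These subjects will be asked to return for repeat Cytosponge administration after the initial administration"), again in 6.1, and in 9.1 footnote 1: "sites will be notified and subjects will be asked to return for repeat Cytosponge administration". SAP 6.6.1.1.1 repeats it with an interval of 30 days, plus or minus 10. The current CIP gives no interval. Section 6.1 adds: "Questionnaires and the endoscopy procedure will not be repeated".

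**Safeguards.** Exclusion 7 in CIP 8.4 bars patients with prior ablation or resection of the oesophagus. CIP 10.1 says: "The current study has been designed to minimize occurrence of these potential risks by use of the exclusion criteria". CIP 7.2 says the criteria were drawn to keep out those at highest risk of bleeding. It also relies on the endoscopy straight after the sponge to retrieve a detached sponge and to deal with any bleeding.

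**Analysis.** Adequacy is the proportion of subjects with at least one columnar cell after up to two sponges, among everyone offered the sponge (CIP 13, SAP 6.6.1.1.1). For same-day ablation, SAP section 4 says: "Patients who are undergoing ablative therapy on the day of Cytosponge testing will have their acceptability data analyzed separately". No corresponding rule exists for adequacy.

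**The concern.** A subject ablated at the study endoscopy leaves it as someone whom exclusion 7 would have turned away beforehand. If the first sample proves inadequate, the rule as written still recalls that subject for a second sponge. That sponge serves the study alone, and the endoscopy that CIP 7.2 counts on as a backstop does not follow it.

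The missing endoscopy is common to every repeat. What sets these subjects apart is that they have also just been treated.

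The gap looks like an oversight in the amendment rather than a decision. Version G separated the Impact of Event scores of same-day-ablation subjects, required them to have biopsies within the previous two months, and edited the repeat procedure by deleting its interval. It did not say whether the repeat applies to them.

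A secondary consequence is that a post-treatment sample may settle the subject's status in two-sample adequacy, part of the second primary objective, with nothing to flag it.

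**Working it through.** **Step 1: does the rule reach treated subjects?** Planned ablation is a recruitment route, and the first sponge precedes the same-day procedure. Any repeat therefore falls after any treatment given at that endoscopy. The only trigger is absence of columnar cells. On the wording, the rule reaches them.

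**Step 2: does any other text exempt them?**

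| Text | What it governs | Exempts? |
|---|---|---|
| CIP 8.4, exclusion 7 | Entry; the 9.1 schedule shows eligibility at the screening/enrolment visit only | No |
| CIP 11.1, postponement of the capsule | Adverse device effects | No |
| CIP 13, 48-hour endoscopy window | The sensitivity analysis, not adequacy | No |
| CIP 9.11, discontinuation by the investigator | General discretion; ablation not mentioned | No |
| SAP 6.3, data judged invalid | General discretion; ablation not mentioned | No |

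**Step 3: how many subjects?** The plan gives no figure to reproduce. It states no adequacy target, ablation share, first-sample failure rate or enrolment under version G. Assumptions:

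- Enrolment under version G: about 100, because the version history says "Increase the sample size by 100 subjects". Range 50 to 150.
- BE share: 50%, the minimum enrolment ratio.
- Ablated share of BE subjects: 25%, borrowed from the high-grade dysplasia share in CIP 13, which is not an ablation rate. High case 50%.
- First-sample failure: 5% to 15%.

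Affected subjects = enrolled × BE share × ablated share × failure rate. Points of adequacy = affected / 275.

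| Enrolled under G | BE subjects | Ablated | Failure | Affected | Points |
|---|---|---|---|---|---|
| 100 | 50 | 25% | 5% | 50 × 0.25 × 0.05 = 0.625 | 0.23 |
| 100 | 50 | 25% | 15% | 50 × 0.25 × 0.15 = 1.875 | 0.68 |
| 100 | 50 | 50% | 15% | 50 × 0.50 × 0.15 = 3.75 | 1.36 |
| 50 | 25 | 25% | 5% | 25 × 0.25 × 0.05 = 0.31 | 0.11 |
| 150 | 75 | 25% | 15% | 75 × 0.25 × 0.15 = 2.81 | 1.02 |

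The counts are proportional to the BE share. The 25% GERD floor allows up to 75% BE, which would multiply every row by 1.5; the largest becomes 3.75 × 1.5 = 5.6. Treatment given between day 4 and a repeat was never covered by the deleted exclusion, so counting only version G enrolment may slightly understate the number.

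**Step 4: scale.** If adequacy were 90% (assumption), its 95% half-width at n = 275 is 1.96 × sqrt(0.9 × 0.1 / 275) = 0.035, or 3.5 points. The points in the table are shares of subjects whose status would depend on a post-treatment sample. They are not estimates of bias.

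**The case against.** The other side has five arguments.

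1. **The instructions for use may settle it.** CIP 7.2 and 7.7 tie administration to them, and a contraindication there would also govern the repeat. They are not among the documents, so this cannot be checked. No reason is given for exclusion 7, which may exist to protect the diagnostic comparison. A reader might infer that a sponge after ablation is a known hazard, but the documents state no such risk. What survives is narrower: CIP 7.2 and 10.1 use the exclusion criteria and the following endoscopy as safeguards, and neither applies at this repeat.
2. **Adequacy needs only one columnar cell, from any source.** The sponge is drawn up from the stomach, and nothing in the documents says that ablation alters the chance of collecting such a cell. A reader might infer that two-sample adequacy is biased. The documents support neither a bias nor a direction, and this argument stands in full.
3. **The trial is a pilot with a descriptive adequacy proportion.** No target or test depends on it. This stands, and limits the point to a minor one.
4. **Discretion exists.** Subjects are asked rather than obliged to return, and the investigator may discontinue them. That reduces the likely number but leaves handling to vary by site, with no rule for classifying the subject.
5. **Resection is not a named recruitment route.** The current text names planned ablation only; resection is admitted through the deletion of the former exclusion. This is correct, so the point rests on ablation, and covering resection in the fix is a precaution.

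**Conclusion.** The gap is real and minor. As written, the plan recalls an ablated subject with an inadequate first sample for a research-only sponge, although treated patients are barred at entry and no endoscopy follows. The case for change is mainly consistency with the plan's own safeguards; the effect on adequacy is secondary.

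About 0 to 4 subjects would be affected with half of subjects having BE, or up to about 1.4 points of two-sample adequacy. Every driving rate is assumed. First-sponge adequacy does not change.

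A reader might arrive at a much larger number by applying a 25% ablated share and a 20% failure rate to the whole trial: 275 × 0.25 × 0.20 = 13.75 subjects, or 5 points. The documents do not support that. The 275 include GERD subjects, and ablation planned within 3 days of the sponge was an exclusion until version G.

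**What to change.** - **CIP 6, 6.1 and 9.1 footnote 1:** state that subjects ablated or resected at or after the study endoscopy are exempt from the repeat sponge.
- **CIP 13 and SAP 6.6.1.1.1:** report two-sample adequacy in two ways, once without these subjects and once with them classified on the first sponge. List any post-treatment sample separately.

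Both figures are needed. Classifying exempt subjects on one sponge while others have two attempts turns their first-sponge failures into certain failures, so that figure should not stand alone.

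The cost is one sentence in three places in the CIP, and one sentence each in CIP 13 and the SAP. The figure that includes these subjects may be slightly lower, because a first-sponge failure among them can no longer be rescued. The figure without them shows how much this matters.

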6.1. Duration

Participation in the study may last about4-10 days after the procedure. Subjects will be contacted 7 days (+/- 3 days) following the Cytosponge and upper endoscopy procedures. During this phone call, adverse events will be assessed and subjects will complete final questionnaire. Participation in the study is complete when subjects have completed the follow-up phone call.

If the Cytosponge tissue specimen is reported as inadequate by the central pathologist, the subject will be asked to return for repeat Cytosponge administration. Only the Cytosponge[™] Cell Collection capsule administration will be repeated. Questionnaires and the endoscopy procedure will not be repeated.

The study is expected to last a total of 24 months (2 years).

